2.1.1.8 Last contact date

Last contact date is defined as the date the patients completes the study or discontinues prematurely. If a patient discontinues the study due to "lost to follow up" the latest date out of assessment dates and event/medication start and end dates will be used as last contact date.

For patients ongoing at time of primary analyses, the cut-off date will be used as last contact date.

2.1.1.9 Stratification factor

Randomization is stratified by risk for COVID-19 disease progression ("high-risk patients" versus "not at high-risk patients").

According to the inclusion criteria for the USA only patients "not at high-risk" will be included in the trial, however in case of protocol deviators US patients could technically be randomized to the high-risk stratum

The stratification of "high-risk" and "not at high-risk" for COVID-19 disease progression will be programmed based on eCRF data for the analysis.

A comparison between COVID-19 disease progression strata recorded in the IRT data, and programmed risk for COVID-19 disease progression (from data reported on the eCRF) will be performed.

Details on stratification definition are included in [Section 5.2](#).

2.1.1.10 Blinding

Site firewalls to prevent unblinding and fully dedicated unblinded clinical teams managing the study will be assigned to ensure that the unblinded treatment assignment, the unblinded IRT outputs, the unblinded treatment administration and handling are overseen in such a way as to ensure patient safety and protocol adherence without risking unblinding the site study staff and the clinical teams. Refer to Pharmacy Manual for IP handling.

This is a patient, investigator, and sponsor-blinded study. Patients, investigators, and the sponsor will remain blinded to study treatment throughout the study, except where indicated below.

The identity of the treatments will be concealed by the use of study drugs that are all identical in packaging, labeling, schedule of administration, appearance, and odor.

Site staff

With the exception of any unblinded site staff identified below, all site staff (including study investigator and study nurse) will be blinded to study treatment throughout the study.

Unblinding a single patient at site for safety reasons (necessary for patient management) will occur via an emergency system in place at the site.

Drug product will be supplied in bulk only for the 3 treatment arms in Part A, therefore an unblinded pharmacist who is independent of the study team will be required in order to maintain the blind. Patient treatment allocation can be obtained by the unblinded pharmacist through the IWR system. Appropriate measures must be taken by the unblinded pharmacist to ensure that the treatment assignments are concealed from the rest of the site staff.

There will be fully blinded drug vials for both the active treatment arm and the placebo arm, in Part B of the trial, so unblinded site and clinical staff would not be needed for Part B.

Sponsor staff or staff engaged to manage the study

The following unblinded sponsor staff or staff (such as CRO) engaged to manage and run the study is required for this study during Part A:

- Unblinded drug accountability monitors
- Unblinded clinical staff managing drug re-supply to site
- Unblinded sample analyst(s) (PK, ADA)

In Part A, unblinded drug accountability monitors are required to review drug accountability, preparation, and allocation remotely. The unblinded monitors will be unblinded through review of source documentation compiled by the unblinded pharmacist, which details treatment allocation to individual patients. These unblinded monitors will also have access to the treatment allocation of the patients through the IWR system.

The following unblinded staff will be applicable to both Part A and Part B:

The external independent data review committee (IDMC) assessing unblinded results and the independent analysis team (independent statistician, independent programmer) will be allowed

to access treatment information for the purpose of creating, reviewing, and assessing unblinded interim results. More details will be provided in an IDMC charter.

An independent pharmacometrician and an independent pharmacokineticist may be unblinded prior to the database lock after all patients complete Day 29 in Part A in order to explore PK. The pharmacometrician and the pharmacokineticist will work independently and will only disclose results once the database is locked after all patients complete Day 29 in Part A at the time of the Part A primary analysis.

Unblinding after the primary analysis database lock in Part A

After the database lock for the primary analysis in Part A, an unblinded study team will perform the analysis and undertake submission related activities. Treatment assignment will continue to remain blinded to all investigators, site personnel, patients and other study team members until all patients have completed the entire study participation and the final database lock for Part A has occurred.

All unblinded staff will otherwise keep randomization lists and data or information that could unblind other study team members confidential and secure until final clinical database lock. Primary analysis results and reports generated prior to the final database lock that would reveal subject-level data will be kept in a secure and restricted area until the end of the study. The detailed procedures for maintaining data integrity after primary analysis database lock will be described in a charter.

Following final database lock all staff may be considered unblinded.

Health authorities will be granted access to unblinded data if needed.

2.2 Analysis sets

The analysis sets are defined as follows:

- **Screened set (SCR):** all unique patients who signed the informed consent (e.g. only the chronologically last screening data is counted in the case of re-screened patients)
- **Randomized set (RAN):** all patients who received a randomization number, regardless of receiving study treatment
- **Full analysis set (FAS):** all patients in the RAN that initiated i.v. infusion of study treatment during the treatment period excluding mis-randomized patients, where mis-randomized patients are defined as cases where IRT contacts were made by the Investigator/qualified site staff either prematurely or inappropriately prior to confirmation of the patient's final randomization eligibility and treatment was not administered to the patient. Following the intention to-treat (ITT) principle, patients will be analyzed according to the randomized treatment arm.
- **Safety set (SS):** all patients who initiated i.v. infusion of study treatment whether being randomized or not. Patients will be analyzed according to the actual dose received. If the actual dose received is not a study dose level, the analyzed dose level will be the next lowest active dose arm.

- **PK analysis set:** all patients with at least one available valid (i.e. not flagged for exclusion) PK concentration measurement, who received any study treatment and with no protocol deviations that impact PK data

Unless otherwise specified, all efficacy analysis will be performed on the FAS and safety analyses will be performed on the SS.

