## **6.6 Additional treatment guidance**

### **6.6.1 Treatment compliance**

The start and end date/time of each infusion as well as any infusion interruptions (stop and restart times) will be documented in the eCRF. The prescribed dosage, timing, and mode of administration may not be changed. Any departures from the intended regimen must be recorded in the eCRFs.

Compliance will not be evaluated for this single-dose study.

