### **6.7.1 Handling of study treatment**

Study treatment must be received by a designated person at the study site, handled and stored safely and properly and kept in a secured location to which only the investigator and designated site personnel have access. Upon receipt, all study treatment must be stored according to the instructions specified in the IMP handling and administration protocol.

Clinical supplies are to be dispensed only in accordance with the protocol. Technical complaints are to be reported to the respective sponsor's Quality Assurance.

Study treatment will be prepared by independent pharmacist or qualified site personnel in order to ensure treatment masking. Following labeling and secondary packaging, the MP0420 IMP is supplied as a sterile solution for i.v. infusion. For clinical administration, the required volume of MP0420 IMP will be calculated as defined in the MP0420 clinical trial protocol. Sterile 0.9 % NaCl infusion bags will be used. First, a sodium chloride solution volume equivalent to the required MP0420 IMP volume will be removed from the bag. Second, the required volume of MP0420 IMP will be injected into the bag. The i.v. infusion will then be performed according to standard clinical procedures using a 0.2 µm in-line filter, and followed by an infusion set flush using 25 mL from a fresh 0.9 % NaCl infusion bag.

Medication labels will be in the local language and comply with the legal requirements of each country. They will include storage conditions for the study treatment but no information about the patient except for the medication number.

The investigator must maintain an accurate record of the shipment and dispensing of study treatment in a drug accountability log. Monitoring of drug accountability will be performed by monitors during site visits or remotely and at the completion of the trial.

At the conclusion of the study, and as appropriate during the course of the study, the investigator will return all unused study treatment, packaging, drug labels, and a copy of the completed drug accountability log will be returned to the CRO as part of the final drug accountability filing.

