## **9 Study discontinuation and completion**

### **9.1 Discontinuation and completion**

#### **9.1.1 Interruption of study drug infusion and study discontinuation**

Study treatment consists of a single dose infusion. In case of interruption of infusion due to AEs, time and relative amount of study drug administered should be recorded in the CRF, as well as restart and end time (as applicable). Adverse event should be captured in appropriate CRF. Treatment of AEs should follow standard of care (symptomatic treatment).

Infusion of study drug must be interrupted or stopped under the following circumstances:

- Patient/guardian decision.
- Suspected hypersensitivity reaction occurs, including any of the following: fever, chills, dyspnea, headache, myalgia, hypotension. Immediate interruption of the infusion to administer study treatment is required in such cases. In case of fever, restart of infusion is permitted under close medical surveillance if the fever subsides with antipyretic treatment. In case of chills, dyspnea, headache or myalgia, restart of infusion is permitted under close medical surveillance if the event was already a noted symptom of COVID-19 at study enrollment and it subsides without treatment within 15 minutes.
- Emergence of any other infusion related reaction: anaphylaxis, angioedema, urticaria, rash, administration site reaction. Immediate interruption of the infusion to administer study treatment is required in such cases. Restart of infusion is not recommended.

Patients who discontinue study treatment or who decide they do not wish to participate in the study further should NOT be considered withdrawn from the study UNLESS they withdraw their consent (see [Section 9.1.2](#) ‘Withdrawal of Informed Consent’ section). **Where possible, they should return for the assessments indicated** in the Assessment Schedule. If they fail to return for these assessments for unknown reasons, every effort (e.g., telephone, e-mail, letter) should be made to contact the patient/pre-designated contact as specified in the lost to follow-up section. This contact should preferably be done according to the study visit schedule.

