#### **10.1.6 Reporting of study treatment errors**

Medication errors are unintentional errors in the prescribing, dispensing, administration or monitoring of a medicine while under the control of a healthcare professional, participant or consumer (European Medicines Agency [EMA] definition).

Study treatment errors and uses outside of what is foreseen in the protocol will be recorded on the appropriate CRF irrespective of whether or not associated with an AE/SAE and reported to Safety only if associated with an SAE.

For more information on AE and SAE definition and reporting requirements, please see the respective sections.

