### 12.1 Analysis sets

The analysis sets are defined as follows:

- **Screened set (SCR):** all unique patients who signed the informed consent (e.g., only the chronologically last screening data is counted in the case of re-screened patients)
- **Randomized set (RAN):** all patients who received a randomization number, regardless of receiving study treatment
- **Full analysis set (FAS):** all patients in the RAN that initiated i.v. infusion of study treatment during the treatment period excluding mis-randomized patients, where mis-randomized patients are defined as cases where IRT contacts were made by the investigator/qualified site staff either prematurely or inappropriately prior to confirmation of the patient's final randomization eligibility and treatment was not administered to the patient
- **Safety set (SS):** all patients who initiated i.v. infusion of study drug

- **PK analysis set:** all patients with at least one available valid (i.e., not flagged for exclusion) PK concentration measurement, who received any study treatment and with no protocol deviations that impact PK data
- For the FAS following the intention to-treat (ITT) principle, patients will be analyzed according to their randomized treatment assignment. Unless otherwise specified, all efficacy analysis will be performed on the FAS.

For the SS following the per-protocol (PP) principle, patients will be analyzed according to the treatment received. Unless otherwise specified, all safety analyses will be performed on the SS.

Important protocol deviations for exclusion from PK analysis set may be identified by the clinical team before the primary analysis and final database lock in Part A and interim and final database lock in Part B.

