Figure 2-1	Candidate models for ensovibep dose.....	25

List of abbreviations

ADA	Anti-Drug Antibody
AE	Adverse Event
AESI	Adverse Event of Special Interest
ANCOVA	Analysis of Covariance
COVID-19	Coronavirus Disease 2019
CSR	Clinical Study Report
CTCAE	Common Toxicity Criteria for Adverse Events
DBL	Database Lock
eCRF	Electronic Case Report Form
eCRS	Electronic Case Retrieval Sheet
FAS	Full Analysis Set
FDA	Food and Drug Administration
FPFV	First Patient First Visit
IA	Interim Analyses
IDMC	Independent Data Monitoring Committee
IRR	Infusion-related Reactions
ITT	Intention-to-treat
MCS	Mental Component Summary
MedDRA	Medical Dictionary for Drug Regulatory Affairs
PCS	Physical Component Summary
PD	Pharmacodynamics
PK	Pharmacokinetics
PP	Per-Protocol
PRO	Patient-Reported Outcomes
PT	Preferred Term
RAN	Randomized Set
RT-PCR	Real Time Polymerase Chain Reaction
SAE	Serious Adverse Event
SAP	Statistical Analysis Plan
SAS	Statistical Analysis System
SARS-CoV-2	Severe Acute Respiratory Syndrome Coronavirus 2
SCR	Screened Set
SF-36	Short Form 36 Health Survey Questionnaire
SMQ	Standard MedDRA Query
SOC	System Organ Class
SS	Safety Set
TEAE	Treatment-emergent Adverse Event

1 Introduction

This document presents the detailed statistical analysis plan (SAP) for Study MP0420-CP302 (CSKO136A12201J), “A randomized, double-blind, placebo-controlled, multicenter study of ensovibep (MP0420) in ambulatory adult patients with symptomatic COVID-19.”

Following the operationally seamless design, analysis of Part A and Part B will be handled separately (e.g., primary, secondary, and exploratory analyses in Part A will be performed only on Part A patients and primary, secondary, and exploratory analyses in Part B will be performed only on Part B patients).

This SAP will include the details for the clinical study report (CSR) analysis of Part A and Part B. In this version, the full details for the CSR analysis of Part A is provided. An outline of the protocol-specified CSR analysis of Part B is provided in the SAP. Further details will be provided in a SAP amendment prior to first patient first visit (FPFV) of Part B.

The analysis for Part A is performed in two parts:

- **Part A primary analysis:** performed when all patients enrolled completed Day 29 or discontinued prematurely and have viral load data up to Day 8; the analysis will include available data on the day of cutoff. Further details are provided in [Section 2.14](#).

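### The Safety Set rule in SAP 2.2, read literally, moves every permanently incomplete active infusion in Part A to a lower dose arm or to no arm

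*SAP*

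**What the plan says.** SAP 2.2 admits to the Safety Set everyone in whom the infusion was initiated; completion is not required. Patients are classified by actual dose received, with this rule for off-level amounts: "If the actual dose received is not a study dose level, the analyzed dose level will be the next lowest active dose arm". SAP Table 5.8-1 removes from the set only patients who took no study drug. Protocol 12.1 is less specific and says that "patients will be analyzed according to the treatment received". SAP section 4 declares no change to the protocol's analyses.

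Protocol 9.1.1 lists circumstances in which the infusion must be interrupted or stopped. For one group of infusion-related reactions it adds: "Restart of infusion is not recommended". It also has the amount given documented: "In case of interruption of infusion due to AEs, time and relative amount of study drug administered should be recorded in the CRF".

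Safety Set tables by treatment include study drug discontinuation (SAP 2.4.1), TEAEs leading to discontinuation (SAP 2.8.1) and AESIs (SAP 2.8.1.1). SAP 2.5.2 names AESIs, AEs and SAEs among the grounds for selecting the Part B dose.

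**The concern.** Treatment is a single infusion, so discontinuing study drug means stopping that infusion before the full dose is in. If actual dose received means the amount infused, a patient enters the discontinuation tables by the same event that removes the patient from the assigned dose column. The rule and the tables then work against each other.

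Infusion site and hypersensitivity reactions of CTCAE grade 2 or higher are AESIs, and reactions of these kinds are also reasons to stop. Those that permanently stop a 600 mg infusion would be tabulated at a lower dose or in no arm, so the highest dose would look cleaner than it was in tables used for dose selection. Stopped placebo infusions keep their column, so active and placebo arms would be handled differently.

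**Working it through.** The plan gives no figure to reproduce. The check applies the rule as written and then illustrates its effect.

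**Inputs from the documents.** Dose levels of 75, 225 and 600 mg, one infusion over 60 minutes, about 100 patients per arm (Protocol sections 3 and 12.8.1); the classification rule (SAP 2.2).

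**Assumed.** Constant flow, no restart, the same true stop rate in each active arm, and stop times uniform over 60 minutes.

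**Step 1: the literal rule.** Analysed arm = the largest of {75, 225, 600} mg not above the amount infused, with no arm below 75 mg because the fallback must be an active arm. Amount infused = dose × minutes / 60.

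- 600 mg runs at 600/60 = 10 mg/min. It reaches 75 mg at 7.5 min and 225 mg at 22.5 min.
- 225 mg runs at 225/60 = 3.75 mg/min. It reaches 75 mg at 20 min.
- 75 mg stays below 75 mg until complete.

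| Arm started | Goes to 225 mg | Goes to 75 mg | No arm |
|---|---|---|---|
| 600 mg | stop from 22.5 to <60 min | stop from 7.5 to <22.5 min | stop before 7.5 min |
| 225 mg | – | stop from 20 to <60 min | stop before 20 min |
| 75 mg | – | – | any stop |

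Even 590 of 600 mg (59 min) is analysed as 225 mg. The cut-points in minutes need constant flow. The direction does not: no infusion that falls short of its full dose stays in its own arm.

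**Step 2: expected counts with s stops per active arm.** Uniform stop times give these shares:

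- 600 mg: 37.5/60 = 62.5% to 225 mg, 15/60 = 25% to 75 mg, 7.5/60 = 12.5% to no arm.
- 225 mg: 40/60 = 66.7% to 75 mg, 20/60 = 33.3% to no arm.
- 75 mg: 100% to no arm.

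The columns are therefore 600 = 0; 225 = 0.625s; 75 = 0.25s + 0.667s = 0.917s; no arm = 0.125s + 0.333s + s = 1.458s.

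| s per 100 | Dose-prepared reading (600/225/75/none) | Literal reading (600/225/75/none) |
|---|---|---|
| 1 | 1/1/1/0 | 0/0.63/0.92/1.46 |
| 2 | 2/2/2/0 | 0/1.25/1.83/2.92 |
| 5 | 5/5/5/0 | 0/3.13/4.58/7.29 |

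**Step 3: tabulated percentages at s = 2.** Each column keeps 98 completed infusions and gains those moved in: 0/98 = 0%; 1.25/(98 + 1.25) = 1.26%; 1.83/(98 + 1.83) = 1.84%. The true value is 2% in each arm.

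**Step 4: sensitivity at s = 2.**

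- All stops at 22.5 min or later: 0/2/2/2. All before 7.5 min: 0/0/0/6.
- If amounts below 75 mg are put in the 75 mg arm instead of no arm: 0/1.25/4.75/0, and the 75 mg percentage becomes 4.75/(98 + 4.75) = 4.6%.
- A stopped infusion could stay at 600 mg only if the full dose was already in. With a bag overfilled by 5% (630/60 = 10.5 mg/min), that needs a stop after 600/10.5 = 57.1 min, which is 4.8% of uniform stop times, or 0.10 of 2 stops. At 10% overfill it needs a stop after 600/11 = 54.5 min: 9.1%, or 0.18 of 2 stops.

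The 225 and 75 mg counts depend on timing and on the handling of amounts below 75 mg, so no dose trend is claimed. The 600 mg column is zero or nearly zero in every variant.

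**The case against.** The best answer is that the sentence was written for preparation or dispensing errors. It follows the clause about patients treated without being randomized, and it speaks of dose levels and arms. Part A drug comes as 15 mg/mL in 10 mL vials (150 mg per vial), in bulk, and is made up at site: "Study treatment will be prepared by independent pharmacist or qualified site personnel in order to ensure treatment masking". An off-level preparation is therefore a natural target for such a rule. Protocol 12.1 and SAP section 4 point the same way, and a reading that empties the 600 mg column of two planned tables is probably not the intended one. All of this stands as evidence of intent. None of it is written in the SAP, where two competent programmers could produce different tables. Even on this reading, a preparation below 75 mg has no stated arm.

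The size is also open to challenge. No stop rate is given, Protocol 9.1.1 allows some interrupted infusions to restart, and interruptions that are later completed are unaffected. The illustration at 2 per 100 means 6 stopped active infusions. If all were moderate to severe hypersensitivity or injection reactions, that would meet the pooled enrollment hold in Protocol 9.1.4 (6 or more patients). That hold can be lifted, and milder or non-AE stops do not count towards it, so it is not a cap.

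Finally, listings show each case, dose selection also uses MCP-Mod, clinical events and symptoms, and the FAS analyses are untouched. These points limit the harm but do not correct the by-dose safety tables.

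**Conclusion.** The concern holds. SAP 2.2 leaves a key term undefined and, on its plain meaning, takes every permanently incomplete active infusion out of its own arm. Discontinuations and TEAEs leading to them would then be essentially absent at 600 mg, and AESIs that stop an infusion would move to a lower dose or to no arm.

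That direction needs no assumption about rates or flow; it rests on the amount-infused reading. The size cannot be derived from the documents and may be nil, since the percentages above rest wholly on assumed stop rates and times. Completed infusions at a study dose level, placebo infusions, the pooled hold rules, individual listings, FAS efficacy and MCP-Mod are not affected. This should be fixed before the Part A primary analysis database lock, so that the choice between readings is not made after unblinding.

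**What to change.** In SAP 2.2:

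- Define the Safety Set arm as the dose level prepared and started.
- Keep incomplete infusions in that arm, with a flag.
- Limit the rule on the next lowest active arm to preparations that were themselves not at a study dose level.
- State the arm for a preparation below 75 mg, for example shown with 75 mg and flagged.
- Align the wording with Protocol 12.1.

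Carry the same definition into the Part B amendment that SAP section 1 already plans: "Further details will be provided in a SAP amendment prior to first patient first visit (FPFV) of Part B".

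The cost is two or three sentences and one derivation. The arm and the flag need only the dose prepared and the infusion record. Protocol 6.6.1 has start, end and interruption times entered and adds: "Any departures from the intended regimen must be recorded in the eCRFs". Protocol 10.1.6 covers preparation errors: "Study treatment errors and uses outside of what is foreseen in the protocol will be recorded on the appropriate CRF". The amount given is explicitly required only for interruptions due to AEs (Protocol 9.1.1). For other stops it can be listed where available or estimated from the recorded times.
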